2.1. Study Objectives

To explore the overall safety profile of VM202 over the long-term as well as the durability of pain relief in subjects enrolled in the VMDN-003 trial.

- To evaluate the long-term safety of IM administration of VM202 in subjects with painful diabetic neuropathy (DPN)
- To evaluate the durability of efficacy of IM administration of VM202 in subjects with painful DPN in the lower extremities.

2.2. Study Endpoints

2.2.1. Safety Endpoints

The primary endpoint is the difference in long-term safety – defined as occurrence of adverse events – observed between subjects receiving VM202 versus subjects receiving placebo in the VMDN-003 study.

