5.6. STUDY ENDPOINTS

5.6.1. PRIMARY ENDPOINTS

The primary endpoint is the difference in long-term safety – defined as occurrence of adverse events - observed between subjects receiving VM202 versus subjects receiving placebo in the VMDN-003 study.

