5.6.3. ANALYSIS METHODS

The statistical analyses will be descriptive only and reported using summary tables, figures, and listings. All summaries will be derived based on available data. The average 24-hour pain score for a visit will be considered as missing if fewer than 5 of 7 days of Daily Pain and Sleep Interference Diary entries are provided. No imputation will be performed for missing values. Summary tables will present results by treatment group (i.e., VM202 and Placebo) both within and across the randomization stratification factor (i.e., baseline use of gabapentin and/or pregabalin) values. Continuous variables will be summarized using the number of non-missing values, mean, standard deviation, median, minimum and maximum values. Categorical data will be summarized using the number of observations and percentages. Summary plots of efficacy data will present mean values with standard error bars.

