4.1. Introduction

Data processing, tabulation of descriptive statistics, calculation of inferential statistics, and graphical representations be performed primarily using SAS (release 9.4 or higher). If the use of other software is warranted, the final statistical methodology report will detail what software was used for what purposes.

Continuous (quantitative) variable summaries will include the number of subjects (n) with non-missing values, mean, standard deviation (SD), median, minimum, and maximum. Other statistics such as coefficient of variation (%CV), quartiles, confidence intervals (CIs), and number of missing values may be added as appropriate.

Categorical (qualitative) variable summaries will include the frequency and percentage of subjects who are in the particular category or each possible value. In general, the denominator for the percentage calculation will be based upon the total number of subjects in the study population within each treatment group, unless otherwise specified. The denominator for by-visit displays will be the number of subjects in the relevant study population with non-missing data at each visit.

The minimum and maximum will be reported with the same degree of precision (ie, the same number of decimal places) as the observed data, unless that precision exceeds two decimal places. If the precision does exceed two decimal places, the minimum and maximum will be reported with two decimal places. Measures of location (mean and median) will be reported to one degree of precision more than the observed data and measures of spread (SD) will be reported to two degrees of precision more than the observed data.

Percentages will be presented to one decimal place, unless otherwise specified.

Summary tables will present results by treatment group (i.e., VM202 and Placebo) both within and across the randomization stratification factor (i.e., baseline use of gabapentin and/or pregabalin) values.

Unless otherwise indicated, all statistical tests will be conducted at the 0.05 significance level using 2-tailed tests, and P values will be reported. Corresponding 95% confidence intervals (CIs) will be presented for statistical tests.

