9.1. Adverse Events

Adverse events will be coded using the MedDRA coding thesaurus (version 21.0). All AEs recorded in the clinical database starting after the last visit on the VMDN-003 study will be considered a treatment-emergent adverse event (TEAE). All AE summary tables will include the number and percentage of subjects with an AE within a category, system organ class (SOC), and preferred term.

An overall summary of the number and percentage of subjects with TEAEs will be provided by treatment group. Frequencies and percentages of the following will be included: subjects with any TEAE, subjects with any TEAE leading to discontinuation, subjects with any TEAE leading to death, and subjects with any serious treatment-emergent AE (SAE).

The incidence of TEAEs will be summarized with frequencies and percentages by the following:

- SOC and PT
- SOC and PT by maximum severity
- SOC and PT by relationship to study medication
- SOC and PT by relationship to injection procedure.
- SAEs by SOC and PT
- AEs of special interest by SOC and PT

There are 4 types of AEs of special interest (AESI):

- Ophthalmological events that could potentially suggest causality related to HGF and its angiogenic potential
- Acute cardiac events

- Foot ulcers
- AEs related to pregabalin or gabapentin and their occurrence rates with in conjunction with VM202

Adverse event data will be summarized by treatment group and by treatment group within baseline gabapentin and pregabalin use.

All adverse events will be presented in a listing.

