Same shell as Table 14.2.1.1, only include Day 270 and Day 365 timepoints. Update headers from 'CFB' to 'CFD270' and '%CFD270'. Drop the [1] footnote.

Update abbreviation footnote to say CFD270 = change from day 270 visit.

Table 14.2.1.1.4

Summary of Change from Day 270 Average 24-hour Pain Score by Gabapentin and/or Pregabalin use at Baseline ITT Population

Same shell as Table 14.2.1.1, add a row at the top of table reading "Group: Gabapentin and/or Pregabalin Use". Once all records from group are summarized, update row text to "Group: No Gabapentin and/or Pregabalin Use" and start table on a new page.

Helixmith Co., Ltd. Protocol VMDN-003b

CONFIDENTIAL

Page x of y <Version>

Table 14.2.1.1.5 Mean Change from Baseline in Average 24-hour Pain Score by Study Visit and Treatment Tabulation of Fitted Summary Statistics from MMRM ITT Population

Study Visit Statistic [1]	Placebo (N=XX)	VM202 (N=XX)
Day 90		
n	XX	XX
LS Mean Change from Baseline (SE)	XX.X (X.XX)	XX.X (X.XX)
(95% CI for LS Mean Change from Baseline)	(XX.X, XX.X)	(XX.X, XX.X)
P value for LS Mean Change from Baseline) [2]	X.XXXX	X.XXXX
LS Mean Difference from Placebo (SE)		XX.X (X.XX)
(95% CI for Difference from Placebo)		(XX.X, XX.X)
P value for Difference from Placebo [3]		X.XXXX
Day 180		
n	XX	XX
LS Mean Change from Baseline (SE)	XX.X (X.XX)	XX.X (X.XX)
(95% CI for LS Mean Change from Baseline)	(XX.X, XX.X)	(XX.X, XX.X)
P value for LS Mean Change from Baseline) [2]	x.xxxx	X.XXXX
LS Mean Difference from Placebo (SE)		XX.X (X.XX)
(95% CI for Difference from Placebo)		(XX.X, XX.X)
P value for Difference from Placebo [3]		X.XXXX
Continu	e for Day 270 and Day 365	

Abbreviation: CI = confidence interval; LS = least squares; SE = standard error.

Note: A negative value of change means an improvement, and a positive value of change means deterioration. Subjects are summarized by randomized treatment. The baseline value is the average 24-hour pain score from the diary collected prior to Day 0.

[1] Estimates for LS means and accompanying 95% CIs and P values are from a linear mixed-effects model for repeated measures (MMRM) with treatment, visit (3-month, 6-month, 9-month, and 12-month visit), treatment-by-visit interaction, and baseline use of gabapentin and/or pregabalin as the main fixed effects, and baseline average 24-hour pain score as a covariate. An unstructured covariance matrix was used to model the within subject correlation.

[2] P value for testing mean change from baseline is zero.

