Note: The denominator for percentage corresponds to the N in each column. N is the number of subjects in the safety population. Subjects are summarized by treatment received in the VMDN-003 study.

[1] P-value from a Cochran-Mantel-Haenszel (CMH) test (stratified by baseline use of gabapentin/pregabalin) comparing VM202 to Placebo. SOURCE: Listing 16.2.6.2

[figure not shown]
[figure not shown]

Table 14.2.5.2
Summary of Patient's Global Impression of Change (PGIC) by Gabapentin and/or Pregabalin use at Baseline mITT Population

Same shell as Table 14.2.5.1, add a row at the top of table reading "Group: Gabapentin and/or Pregabalin Use". Once all records from group are summarized, update row text to "Group: No Gabapentin and/or Pregabalin Use" and start table on a new page. Do not include the CMH test or footnote.

Helixmith Co., Ltd. Protocol VMDN-003b

CONFIDENTIAL

Page x of y <Version>

Table 14.3.1.1.1 Summary of Treatment Emergent Adverse Events Safety Population

Category	Placebo (N=XX) n (%)	VM202 (N=XX) n (%)	Overall (N=XX) n (%)
Subjects with at least one TEAE	XX (XX.X%)	XX (XX.X%)	XX (XX.X%)
Subjects with at least one TEAE related to study medication	XX (XX.X%)	XX (XX.X%)	XX (XX.X%)
Subjects with at least one TEAE related to injection procedure	XX (XX.X%)	XX (XX.X%)	XX (XX.X%)
Subjects with at least one TEAE leading to discontinuation	XX (XX.X%)	XX (XX.X%)	XX (XX.X%)
Subjects with at least one TEAE leading to death	XX (XX.X%)	XX (XX.X%)	XX (XX.X%)
Subjects with at least one SAE	XX (XX.X%)	XX (XX.X%)	XX (XX.X%)

Abbreviations: PT = Preferred Term; SOC = System Organ Class; TEAE = Treatment emergent adverse event; SAE = Serious treatment emergent adverse event; N = Number of subjects in the safety population; n = Number of subjects with events.

Note: The denominator for percentage corresponds to the N in each column. Subjects are summarized by treatment received in the VMDN-003 study. AEs were coded using MedDRA version 21.0. A TEAE is any AE that occurs after the last visit in the VMDN-003 study and pre-existing medical conditions that worsen following the last visit in the VMDN-003 study.

SOURCE: Listing 16.2.7.1

[figure not shown]
[figure not shown]

Table 14.3.1.1.2

Summary of Treatment Emergent Adverse Events by Gabapentin and/or Pregabalin use at Baseline Safety Population

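### The primary endpoint is a between-arm difference in adverse events, but the SAP names no effect measure for it and reports neither the difference nor its precision

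*SAP*

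**What the plan says.** SAP 2.2.1 words the primary endpoint as a contrast: "The primary endpoint is the difference in long-term safety", measured by whether adverse events occur, between those who received VM202 and those who received placebo in VMDN-003. Protocol 5.6.1 has the same definition, with the difference being the one "observed between subjects receiving VM202 versus subjects receiving placebo in the VMDN-003 study".

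Protocol 5.6.3 sets the general method: "The statistical analyses will be descriptive only and reported using summary tables, figures, and listings". Categorical data are to be given as counts and percentages, by treatment group, within and across baseline gabapentin/pregabalin use.

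SAP 9.1 follows that for adverse events: "An overall summary of the number and percentage of subjects with TEAEs will be provided by treatment group". It then lists incidence tables by system organ class and preferred term, severity, relationship, seriousness and special interest. In the overview shell, Table 14.3.1.1.1, the columns are Placebo, VM202 and Overall, and the note reads "The denominator for percentage corresponds to the N in each column".

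SAP 4.1 has one rule on intervals that could apply: "Corresponding 95% confidence intervals (CIs) will be presented for statistical tests". SAP 3.2 says the study was not designed around power and will take as many VMDN-003 subjects as it can.

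**The concern.** A primary endpoint defined as a difference should lead to a reported difference, in a stated measure, with some indication of how well it is estimated. Here the reader gets two percentages side by side. The SAP does not say whether the contrast is a risk difference, a ratio or something else, or which adverse event category carries it.

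The secondary endpoints are better served. The pain score and responder models give a VM202-minus-placebo estimate with a 95% interval at each visit (SAP 8.1), and PGIC gets a stratified p-value (SAP 8.4).

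The risk lies in interpretation. Because the number of participants is left to whoever consents, similar percentages in the two arms could be taken as showing no safety difference when the data are also compatible with a sizeable excess on VM202. That matters most for the special-interest events in SAP 9.1, such as ophthalmological and acute cardiac events, where counts may be low.

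**Working it through.** **1. Does any planned output report the contrast?**

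| Place | Between-arm estimate | Interval |
|---|---|---|
| SAP 9.1 text | none | none |
| Tables 14.3.1.1.1 to 14.3.1.5.2 (TEAEs) | none; n (%) by arm and overall | none |
| Tables 14.3.2.1.1 and 14.3.2.1.2 (SAEs) | none; n (%) | none |
| Tables 14.3.3.1.1 and 14.3.3.1.2 (special interest) | none; n (%) | none |
| Table 14.2.1.1.5 (pain, secondary) | difference in least-squares means | 95% |
| Table 14.2.2.2 (responders) | difference from placebo | 95% |

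**2. Do the general rules fill the gap?** No. The interval rule in SAP 4.1 is tied to statistical tests, and none is planned for adverse events. The optional extra statistics in SAP 4.1 and in the population summary conventions of SAP 13 mention confidence intervals, but under continuous variables. Categorical summaries are frequency and percentage.

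**3. How much precision goes unreported?** The documents give no sample size, allocation ratio or event rate, so there is no planned figure to reproduce. Everything below uses assumed inputs, with equal arms.

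Newcombe hybrid-score interval, with p1 for VM202, p2 for placebo and d = p1 − p2:

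- Wilson limits for each arm: (p + z²/2n ± z√[p(1−p)/n + z²/4n²]) / (1 + z²/n), with z = 1.96.
- Lower limit: d − √[(p1 − l1)² + (u2 − p2)²].
- Upper limit: d + √[(u1 − p1)² + (p2 − l2)²].

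Worked case, 10/50 in each arm: the Wilson limits are 11.2% and 33.0%. So d = 0, and the half-width is √[(20.0 − 11.24)² + (33.04 − 20.0)²] = √(76.7 + 170.0) = 15.7 points.

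| Assumed result | Per arm | Difference (points) | 95% interval |
|---|---|---|---|
| 20% v 20% | 30 | 0 | ±20.2 |
| 20% v 20% | 50 | 0 | ±15.7 |
| 20% v 20% | 100 | 0 | ±11.1 |
| 10% v 4% (5/50 v 2/50) | 50 | +6.0 | −5.0 to +17.7 |
| 0 v 0 | 50 | 0 | ±7.1 |

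**4. Wider range.** The simple Wald half-width, 1.96√[p(1−p)(1/n1 + 1/n2)], with equal rates of 5% to 40% and total N of 60 to 400, runs from 4.3 points (N = 400, 5%) to 24.8 points (N = 60, 40%). With 2:1 allocation it runs from 4.5 to 26.3 points.

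**The case against.** The strongest reply is that the safety tables do what the protocol asks. Protocol 5.6.3 calls for a descriptive analysis with counts and percentages, and SAP 9.1 delivers that by arm and by stratum. On this view it is the efficacy models that depart from the protocol, which is a separate matter, and the contrast with them does not show a fault in the safety plan. This stands as far as testing is concerned: the absence of a hypothesis test is a stated choice. It does not rule out an estimate with an interval, which is itself descriptive.

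A reader might go further and infer that the plan never computes its primary endpoint. The documents do not support that. Table 14.3.1.1.1 prints n, N and percentage for both arms, so the observed difference is one subtraction away. A crude interval can be rebuilt from the same counts, and the by-stratum tables hold what a stratified interval needs for any TEAE, related TEAE and SAE. For those rows the proposal adds prespecification and visible precision; it does not recover lost information.

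A reader might also infer that SAP 4.1 is breached, or that the arms will be small. Neither follows. The interval rule covers tests only. No sample size is stated, and protocol synopsis text invites all 24 US sites. Nor does either document plan a conclusion of no difference.

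Finally, an interval could suggest more certainty than the comparison allows. Participants chose to continue and must have had every injection. The safety population includes screen failures (SAP 5). The TEAE tables count only events starting after the last VMDN-003 visit (SAP 6.1.7), whereas protocol 5.3 collects from Day 0. If that visit is Day 270, the window is 365 − 270 = 95 of 365 days, or 26%. This objection stands, and the limitation should be printed beside the interval.

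**Conclusion.** The point holds as a reporting gap. The primary endpoint is worded as a between-arm difference, but no effect measure is named and no output reports the difference or its uncertainty, while the secondary pain and responder analyses have both. It is not an error in testing, and it does not leave the endpoint unobtainable.

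The size depends on inputs that the documents do not give. Under the assumed rates and arm sizes, equal percentages are compatible with differences of about 11 to 20 points either way at 100 down to 30 per arm. With larger arms and rarer events the uncertainty falls to about 4 points. The gap can be closed inexpensively, and because SAP 1 says the plan is to be filed before any unblinded analysis, the change belongs there.

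**What to change.** - **Measure.** In SAP 9.1, name the risk difference, VM202 minus placebo, by treatment received, as the summary of the primary endpoint. Give a 95% interval (Miettinen-Nurminen or Newcombe) and no p-value, which keeps it within protocol 5.6.3.
- **Main tables.** Add the estimate and interval to Table 14.3.1.1.1 for any TEAE, TEAE related to study medication and SAE, and to the first row of Table 14.3.2.1.1. Give it overall and stratified by baseline gabapentin/pregabalin use.
- **Special-interest events.** One extra column is not enough. Tables 14.3.3.1.1 and 14.3.3.1.2 are titled for serious events and laid out by system organ class and preferred term, with no row for any of the four classes in SAP 9.1. First add one row per class covering all events, serious or not, then add the same column.
- **Footnote.** State that the interval reflects sampling error only, in a self-selected extension cohort, for events starting after the last VMDN-003 visit.

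The minimum alternative is to reword the endpoint in both documents as incidence by arm, which removes the mismatch but leaves precision unreported.

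The cost is some SAP wording and a few table rows and columns, with no new data. The intervals may be wide; showing that is the purpose of printing them.

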2.2.2. Efficacy Endpoints

The secondary efficacy endpoints are:

- The change in the average 24-hour pain score from baseline to the Day 365 follow-up from the Daily Pain and Sleep Interference Diary
- The change in the average 24-hour pain score from the Day 270 to the Day 365 follow-up from the Daily Pain and Sleep Interference Diary
- Patient's Global Impression of Change (PGIC) at the Day 365 follow-up

3. Overall Study Design and Plan

This is a prospective, observational, non-interventional study for long-term follow-up of subjects enrolled in the VMDN-003 study: a phase III, double-blind, randomized, placebo-controlled, multicenter, 9-month study designed to assess the safety and efficacy of VM202 in subjects with painful DPN. Subjects currently enrolled or having recently completed the VMDN-003 trial will be invited to provide informed consent and enroll in this extension study.

After providing consent, subjects will be asked to complete a 7-Day Daily Pain and Sleep Interference diary and one visit 365 ± 14 days after their VMDN-003 Day 0 visit. Diaries will be collected at the visit, along with vital signs, concomitant medications, adverse events, and the PGIC questionnaire.

3.1. Overall Design

3.2. Sample Size and Power

This study was not designed with statistical power in mind and will enroll as many VMDN-003 subjects as possible.

3.3. Study Population

This study will include subjects who are randomized and administered study drug in the VMDN-003 trial, and who are still currently enrolled or within 90 days of having completed the Day 270 visit.

3.4. Treatments Administered

Not applicable.

[figure not shown]
3.5. Method of Assigning Subjects to Treatment Groups

In the safety outputs, subjects will be analyzed using the treatment they received in the VMDN-003 study. Subjects will be analyzed according to treatment received, regardless of original treatment assigned.

In the efficacy outputs, subjects will be analyzed according to randomized treatment on the VMDN-003 study.

3.6. Blinding and Unblinding

Not applicable.

[figure not shown]

3.7. Schedule of Events

A detailed schedule of events for the study is provided in Table 1.

Procedure	Day 270 Up to 14 D prior to Day 365	12M Day 365 ± 14 D
Informed Consent	V	
Safety and Efficacy Parameters		
Vital Signs		1
Concomitant Medications		1
Daily Pain and Sleep Interference Diary		1
PGIC		1
Adverse Events		1

4. Statistical Analysis and Reporting

This SAP is based on the approved clinical study protocol, version C, dated 30-Jul-2019.

This SAP addresses the safety and efficacy objectives of the study and describes the statistical methods that are to be used for the final analysis of the completed study.

The reader of this SAP is encouraged to also read the clinical protocol, DSMB charter, and all other identified documents, for details on the planned conduct of the study. Operation aspects related to the collection and timing of planned clinical assessments are not repeated in this SAP unless relevant to the planned analysis.

4.1. Introduction

Data processing, tabulation of descriptive statistics, calculation of inferential statistics, and graphical representations be performed primarily using SAS (release 9.4 or higher). If the use of other software is warranted, the final statistical methodology report will detail what software was used for what purposes.

Continuous (quantitative) variable summaries will include the number of subjects (n) with non-missing values, mean, standard deviation (SD), median, minimum, and maximum. Other statistics such as coefficient of variation (%CV), quartiles, confidence intervals (CIs), and number of missing values may be added as appropriate.

Categorical (qualitative) variable summaries will include the frequency and percentage of subjects who are in the particular category or each possible value. In general, the denominator for the percentage calculation will be based upon the total number of subjects in the study population within each treatment group, unless otherwise specified. The denominator for by-visit displays will be the number of subjects in the relevant study population with non-missing data at each visit.

The minimum and maximum will be reported with the same degree of precision (ie, the same number of decimal places) as the observed data, unless that precision exceeds two decimal places. If the precision does exceed two decimal places, the minimum and maximum will be reported with two decimal places. Measures of location (mean and median) will be reported to one degree of precision more than the observed data and measures of spread (SD) will be reported to two degrees of precision more than the observed data.

Percentages will be presented to one decimal place, unless otherwise specified.

Summary tables will present results by treatment group (i.e., VM202 and Placebo) both within and across the randomization stratification factor (i.e., baseline use of gabapentin and/or pregabalin) values.

Unless otherwise indicated, all statistical tests will be conducted at the 0.05 significance level using 2-tailed tests, and P values will be reported. Corresponding 95% confidence intervals (CIs) will be presented for statistical tests.

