3.3.1. INCLUSION CRITERIA

Subjects must satisfy all of the following criteria to be included in the study:

- 1. Subjects randomized and dosed in the VMDN-003 study;
- 2. Having received all intramuscular injections of study drug on Days 0, 14, 90, and 104 in the VMDN-003 study;
- 3. Currently in follow-up for the VMDN-003 study or having completed Day 270 within the last 90 days prior to signing consent.

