5.5. ANALYSIS POPULATION

The analysis population will be the safety population, and will include all subjects who sign consent for the safety extension study. Subjects in the analysis population

will be analyzed according to treatment received, regardless of original treatment assignment. The primary analyses of the primary and secondary endpoints will be based on the analysis population.

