5.6.2. SECONDARY ENDPOINTS

The secondary efficacy endpoints are:

- 1. The change in the average 24-hour pain score from baseline to the Day 365 follow-up from the Daily Pain and Sleep Interference Diary;
- 2. The change in the average 24-hour pain score from Day 270 to the Day 365 follow-up from the Daily Pain and Sleep Interference Diary; and
- 3. Patient's Global Impression of Change (PGIC) at the Day 365 follow-up.

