This statistical analysis plan (SAP) describes the planned analysis and reporting for Helixmith Co., Ltd. protocol number VMDN-003b (long-term, prospective, non-interventional, safety extension of a phase III, double-blind, randomized, placebo-controlled, multicenter study to assess the safety and efficacy of VM202 in subjects with painful diabetic neuropathy), version C, dated 30-Jul-2019. Reference materials for this statistical plan include the protocol and the accompanying sample data collection documents. Operational aspects related to collection and timing of planned clinical assessments are not repeated in this SAP unless relevant to the planned analysis.

The structure and content of this SAP provides sufficient detail to meet the requirements identified by the Food and Drug Administration (FDA), European Medicines Agency (EMA), and International Conference on Harmonization (ICH) of Technical Requirements for Registration of Pharmaceuticals for Human Use: Guidance on Statistical Principles in Clinical Trials. All work planned and reported for this SAP will follow internationally accepted guidelines, published by the American Statistical Association and the Royal Statistical Society, for statistical practice.

The planned analyses identified in this SAP may be included in clinical study reports (CSRs), regulatory submissions, or future manuscripts. Also, post-hoc exploratory analyses not necessarily identified in this SAP may be performed to further examine study data. Any post-hoc or unplanned, exploratory analysis performed will be clearly identified as such in the final CSR.

The statistical plan described hereafter is an *a priori* plan. It will be submitted to file prior to any unblinded inferential or descriptive analysis of data pertaining to Helixmith Co., Ltd.'s study VMDN-003b.

2. Study Objectives and Endpoints

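### For efficacy the SAP plans 0.05-level tests, sensitivity imputation and randomised-arm grouping, contrary to protocol version C; it lists no departure and does not label the p-values nominal

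*SAP*

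**What the plan says.** **Protocol.** Section 5.6.3 states: "The statistical analyses will be descriptive only and reported using summary tables, figures, and listings". It continues "All summaries will be derived based on available data" and "No imputation will be performed for missing values". Section 5.5 defines one population, grouped by treatment received, and adds: "The primary analyses of the primary and secondary endpoints will be based on the analysis population". Efficacy falls under that rule, because section 5.6.2 opens its list with "The secondary efficacy endpoints are" and then names pain change from baseline to Day 365, pain change from Day 270 to Day 365, and PGIC at Day 365.

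**SAP.** Sections 1 and 4 identify protocol version C as the basis. Section 4.1 then says that "all statistical tests will be conducted at the 0.05 significance level using 2-tailed tests, and P values will be reported". For efficacy the SAP specifies:

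- a repeated-measures model for pain change and a responder model, each with a confidence interval and p-value for the treatment difference (8.1);
- treatment-by-subgroup interaction tests, with a Gail and Simon test where an interaction is significant (8.2);
- a Cochran-Mantel-Haenszel test for PGIC (8.4);
- multiple imputation, mean-of-the-other-group imputation and logistic imputation as sensitivity analyses (6.1.4);
- grouping by randomised arm, with ITT as the primary efficacy population (3.5 and 5).

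Sections 6.1.2 (covariates), 6.1.3 (multiple comparisons) and 10 (changes from planned analysis) are each marked as not applicable.

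**The concern.** Two documents that claim to describe the same plan give opposite instructions on whether efficacy is tested, whether missing scores are imputed and how subjects are grouped. The section of the SAP in which a reader would look for departures lists none.

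The consequence lies in reporting. SAP section 1 says: "The planned analyses identified in this SAP may be included in clinical study reports (CSRs), regulatory submissions, or future manuscripts". Its labelling rule covers only post-hoc or unplanned analyses, so the planned tests escape it. A p < 0.05 on durability of pain relief could be reported as a prespecified result at the 0.05 level, without the word nominal, although the protocol provides for no test at all.

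**Working it through.** The documents state no sample size, power or error rate for this study, so there is no figure to reproduce. The check compares texts and then counts table shells.

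**1. Can the two documents be reconciled?**

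- *Testing.* No. Descriptive only excludes hypothesis tests. The SAP keeps the descriptive summaries and adds tests to them.
- *Imputation.* No. The protocol makes no exception for sensitivity analyses. Seven outputs use imputed data: Tables 14.2.1.2.1, 14.2.1.2.2, 14.2.1.3.1, 14.2.1.3.2, 14.2.2.3, 14.2.2.4 and 14.2.2.5. Two of them (14.2.1.2.1 and 14.2.1.3.1) are descriptive summaries, which the protocol confines to available data. The main pain model uses observed scores, and the rule requiring 5 of 7 diary days is the same in both documents.
- *Grouping.* The rules differ, but the people are essentially the same. Protocol 3.3.1 requires randomisation and dosing, and also "Having received all intramuscular injections of study drug on Days 0, 14, 90, and 104 in the VMDN-003 study". The change of rule alters a result only if someone received a treatment other than the one assigned. The documents give no such number.

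**2. Does the SAP record this?** Section 10 lists nothing. Section 6.1.2 says covariate adjustment does not apply, yet the 8.1 models adjust for baseline pain and baseline gabapentin/pregabalin use. Tables 14.2.1.14 and 14.2.2.13 call for four added covariates and name three (HbA1c, gender, age). Nothing in section 6.1.3 or elsewhere describes the p-values as nominal.

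**3. How many p-values at Day 365 on protocol secondary endpoints?** Pain-change models, by table title:

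| Type | Models |
|---|---|
| Main model (14.2.1.1.5) | 1 |
| Imputation | 2 |
| mITT | 1 |
| Prohibited-medication exclusions | 2 |
| Treatment-by-subgroup interaction | 3 |
| Extra covariates | 4 |
| Within subgroup (HbA1c, gender, age; 2 levels each) | 6 |
| Total | 19 |

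This is 1 main model, 2 + 1 + 2 + 3 + 4 = 12 reruns and 6 subgroup models. Adding PGIC gives 19 + 1 = 20 between-arm p-values.

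- Low count: the printed interaction shell (14.2.1.8.3) stops at Day 180. If all three interaction tables follow it, 20 − 3 = 17.
- High count: SAP 8.2 also calls for models within the two gabapentin/pregabalin groups, for which there is no model shell. Then 20 + 2 = 22.

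The pain-model shell (14.2.1.1.5) also prints a p-value for each arm's own change from baseline, which the text of 8.1 does not request. By table title that is 19 × 2 = 38 at Day 365. Read literally, the shell cross-references lead only 12 of the 19 models to a shell with that row, giving 12 × 2 = 24, or 22 if 14.2.1.8.3 stops at Day 180. No single within-arm count is secure.

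**4. Chance of at least one p < 0.05 with no effect.** Two secondary endpoints have a p-value row at Day 365: pain change from baseline (main model) and PGIC.

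- Independent tests: 1 − 0.95² = 0.0975, or 9.8%.
- Correlated tests: 1 − P(|Z₁| < 1.96 and |Z₂| < 1.96) for bivariate normal statistics, by numerical integration, gives 9.07% at r = 0.5 and 8.35% at r = 0.7.

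The correlations are assumptions. The 18 reruns and subgroup models are left out because they are strongly correlated with the main model and are not separate endpoints.

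**The case against.** The best defence is that a SAP may add detail to a protocol, and that this one was to be filed as an a priori plan before any unblinded analysis (section 1). It calls the aim exploratory (2.1) and says the study was not designed for power (3.2). No success rule is stated and the primary endpoint is only summarised, so marking multiplicity as not applicable is defensible.

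Most of that stands. The tests are prespecified, and a reader who inferred data-driven testing would be wrong. No multiplicity procedure is needed. But the protocol's exclusions are explicit, so adding tests and imputation reverses them, and neither the exploratory aim nor the lack of power is attached to the p-values.

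Four stronger readings are tempting and not supported:

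- *77 tests of secondary endpoints.* The pain models give 19 × 4 visits + 1 = 77, but 19 × 3 = 57 of these are at Days 90, 180 and 270. Protocol 5.6.2 defines the pain endpoints only at Day 365.
- *Three tested endpoints, 1 − 0.95³ = 14.3%.* SAP 8.1 gives the Day 270 to 365 comparison a contrast statement, but no shell has a p-value row for it.
- *A declaration that nothing departs from the protocol.* Section 10 does not name the protocol as its comparator. It is accurate to say that it lists no change.
- *An ITT set that hides who is in it.* SAP section 5 already limits it to subjects who consented to the extension. The note to Table 14.2.5.1, which cites the safety population and treatment received under an ITT title, is a shell slip to correct at programming.

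**Conclusion.** The conflict is real and should be fixed. Protocol 5.5 and 5.6.3 cannot be followed together with SAP 3.5, 4.1, 5, 6.1.4 and 8.1 to 8.4, and the SAP neither records the departures nor labels the resulting p-values.

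Its reach is limited to efficacy. The adverse-event endpoint is summarised by counts and percentages on the safety population by treatment received (SAP 9 and 9.1), as the protocol intends. Imputation is confined to sensitivity analyses. The size is about 20 between-arm p-values at Day 365 (17 to 22), only two of them main comparisons on separate endpoints, plus within-arm p-values of uncertain number. The error rate of 8 to 10% is illustrative: it rests on treating those two endpoints as the family and on assumed correlations from 0 to 0.7.

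**What to change.** 1. In SAP section 10, list the testing, imputation and grouping departures from protocol 5.5 and 5.6.3, with reasons, and align the protocol if it is amended. Alternatively, remove the tests and the imputation.
2. Correct section 6.1.2 to name the model covariates, and make the shells for Tables 14.2.1.14 and 14.2.2.13 agree with the three covariates they list.
3. If the tests stay, replace section 6.1.3 with: *No multiplicity control is applied. All p-values, between-arm and within-arm, are nominal and exploratory and will be reported as such.*

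The cost is SAP wording, with no new data. A protocol amendment is needed only if that route is chosen, with IRB approval first where the change affects subject safety or study validity (protocol section 11). Removing the tests instead would delete many table shells. The price of keeping them is that their p-values can no longer be presented as significance findings.
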